8.3.3 Questionnaire

For assessment of self-reported daily impairments, all subjects will be asked to complete the EQ-5D questionnaire. Completion of the EQ-5D takes 5 to 10 minutes. The EQ-5D is a generic classification system used to characterize current health states of individuals, for which “of the shelf” utilities from members of the general public are available in the literature. The EQ-5D consists of 5 domains (mobility; self-care; usual activity; pain/discomfort; anxiety/depression) and a Visual Analogue Scale (EQ-VAS). Subjects are asked to indicate their level of health by checking one of three levels of functioning for each domain. For the VAS, subjects draw a line from a box to the point on the thermometer like-scale corresponding to their health state, 0-100 (100 is best health state).

Outcome of the test is a unitless number between 0 and 1 that be calculated from an online calculator at the website of the developer of the test (euroqol.org), with 1 being the best possible outcome and 0 the worst.

Subjects will return the EQ-5D personally or via mail. The investigator will check whether all questionnaires are fully completed and will correct, if necessary, in consultation with the subject.

If HRCT, as ordered by attending pulmonologist as part of regular care for persisting pulmonary complaints, is repeated 8-10 months after timepoint T₀, 6 minute walking test will be performed again.

8.3.4 Blood sample collection

At the time of FAPI PET/CT, 30ml of blood for measurement of circulating Extracellular Matrix (ECM) markers and inflammatory parameters (C-reactive protein, leucocyte count, lymphocyte count, erythrocyte sedimentation rate) will be drawn from the intravenous catheter. ECM markers consist of several biomarkers that have been shown to predict lung function decline and mortality in pulmonary fibrosis (16). Serum samples will be labeled with a unique code which is made up of FAPI-COVID, the subject's study number and date of drawing, stored at -80°C and sent for further analysis after collection of all samples. The samples will be accessible during the study period to the investigators. The encryption key is accessible to the coordinating investigator only.

8.3.5 Nasal epithelium collection

Nasal epithelium collection will be performed as follows. Subjects are asked for their favourable nostril to perform the procedure. Subjects are then asked to blow their nose and attempt to remove any mucous from the nose. 1 mL of Lidocaine (10mg/mL) is collected in a 1mL or 2 mL syringe. Subjects are asked to make the sound of the letter K repeatedly while

0.5mL of lidocaine is injected into the nostril (aiming toward the inferior turbinate) to numb the area to be brushed. The subjects are asked to lean forward and any remaining Lidocaine is collected onto a tissue. The steps are repeated with another 0.5mL of lidocaine. After a few minutes, using the speculum to open the nostril, the lateral area underneath the inferior turbinate is the brushed for 3 seconds and the brush is placed in 2 mL screw-cap Eppendorf tube containing 1.5 mL of RNAProtect Cell solution. The brush is then cut into the tube using a wire cutter cleaned with RNase Zap and alcohol.

8.3.6 Physical exercise

All subjects will perform a 6-minute walking test at the same visit of the FAPI PET/CT. The test will be taken according to guidelines (17). Heartrate and peripheral oxygenation will be measured before and after the test. Outcome of the test is total walking distance in meters. The whole test takes approximately 10 minutes.

If HRCT, as ordered by attending pulmonologist as part of regular care, is repeated 8-10 months after timepoint T₀ for persisting pulmonary complaints, 6 minute walking test will be performed again.

8.4 Withdrawal of individual subjects

Subjects can leave the study at any time for any reason if they wish to do so without any consequences. The investigator can decide to withdraw a subject from the study for urgent medical reasons.

8.5 Replacement of individual subjects after withdrawal

Replacement for subjects after withdrawal from the study if the patients withdraws after inclusion.

8.6 Follow-up of subjects withdrawn from treatment

Patients that withdraw from the study will not be followed up.

8.7 Premature termination of the study

Not applicable.

9. SAFETY REPORTING

9.1 Temporary halt for reasons of subject safety

In accordance to section 10, subsection 4, of the WMO, the sponsor will suspend the study if there is sufficient ground that continuation of the study will jeopardise subject health or safety. The sponsor will notify the accredited METC without undue delay of a temporary halt including the reason for such an action. The study will be suspended pending a further positive decision by the accredited METC. The investigator will take care that all subjects are kept informed. Unexpected incidental findings on the ⁶⁸Ga-FAPI PET/CT will be noted and reported to the head practitioner of the patient who inform the patient as well.

9.2 AEs, SAEs and SUSARs

9.2.1 Adverse events (AEs)

Adverse events are defined as any undesirable experience occurring to a subject during the study, whether or not considered related to the investigational product and trial procedure. All adverse events reported spontaneously by the subject or observed by the investigator or his staff will be recorded.

9.2.2 Serious adverse events (SAEs)

A serious adverse event is any untoward medical occurrence or effect that

- results in death;
- is life threatening (at the time of the event);
- requires hospitalisation or prolongation of existing inpatients' hospitalisation;
- results in persistent or significant disability or incapacity;
- is a congenital anomaly or birth defect; or
- any other important medical event that did not result in any of the outcomes listed above due to medical or surgical intervention but could have been based upon appropriate judgement by the investigator.

An elective hospital admission will not be considered as a serious adverse event.

The investigator will report all SAEs to the sponsor without undue delay after obtaining knowledge of the events, except for the following SAEs:

The sponsor will report the SAEs through the web portal *ToetsingOnline* to the accredited METC that approved the protocol, within 7 days of first knowledge for SAEs that result in death or are life threatening followed by a period of maximum of 8 days to complete the initial preliminary report. All other SAEs will be reported within a period of maximum 15 days after the sponsor has first knowledge of the serious adverse events.

9.2.3 Suspected unexpected serious adverse reactions (SUSARs)

Adverse reactions are all untoward and unintended responses to an investigational product related to any dose administered.

Unexpected adverse reactions are SUSARs if the following three conditions are met:

1. the event must be serious (see chapter 9.2.2);
2. there must be a certain degree of probability that the event is a harmful and an undesirable reaction to the medicinal product under investigation, regardless of the administered dose;
3. the adverse reaction must be unexpected, that is to say, the nature and severity of the adverse reaction are not in agreement with the product information as recorded in:
 - Summary of Product Characteristics (SPC) for an authorised medicinal product;
 - Investigator's Brochure for an unauthorised medicinal product.

The sponsor will report expedited the following SUSARs through the web portal *ToetsingOnline* to the METC:

- SUSARs that have arisen in the clinical trial that was assessed by the METC;
- SUSARs that have arisen in other clinical trials of the same sponsor and with the same medicinal product, and that could have consequences for the safety of the subjects involved in the clinical trial that was assessed by the METC.

The remaining SUSARs are recorded in an overview list (line-listing) that will be submitted once every half year to the METC. This line-listing provides an overview of all SUSARs from the study medicine, accompanied by a brief report highlighting the main points of concern.

The expedited reporting of SUSARs through the web portal Eudravigilance or *ToetsingOnline* is sufficient as notification to the competent authority.

The sponsor will report expedited all SUSARs to the competent authorities in other Member States, according to the requirements of the Member States.

The expedited reporting will occur not later than 15 days after the sponsor has first knowledge of the adverse reactions. For fatal or life-threatening cases the term will be maximal 7 days for a preliminary report with another 8 days for completion of the report.

9.3 Annual safety report

In addition to the expedited reporting of SUSARs, the sponsor will submit, once a year throughout the clinical trial, a safety report to the accredited METC, competent authority, and competent authorities of the concerned Member States.

This safety report consists of:

- a list of all suspected (unexpected or expected) serious adverse reactions, along with an aggregated summary table of all reported serious adverse reactions, ordered by organ system, per study;
- a report concerning the safety of the subjects, consisting of a complete safety analysis and an evaluation of the balance between the efficacy and the harmfulness of the medicine under investigation.

9.4 Follow-up of adverse events

All AEs will be followed until they have abated, or until a stable situation has been reached. Depending on the event, follow up may require additional tests or medical procedures as indicated, and/or referral to the general physician or a medical specialist.

SAEs need to be reported until the end of the study within the Netherlands, as defined in the protocol.

9.5 Data Safety Monitoring Board (DSMB)

Considering the low risk associated with this study, a DSMB will not be instituted.

10. STATISTICAL ANALYSIS

Normally distributed quantitative variables will be presented with the mean, standard deviation and 95 % confidence interval. Non-normally distributed data will be presented with median and interquartile range. Outcomes of primary and secondary study parameters will be exploratory outcomes.

10.1 Primary study parameter(s)

Descriptive statistics will be used to analyze the degree of Fibroblast Activation Protein expression on ^{68}Ga -FAPI PET/CT, expressed as wTL-FAPI and wFAPI-MAV. Correlations between FAPI-PET/CT findings and HRCT findings will be assessed using Pearson's correlation coefficient or Spearman's rank-order correlation. A p-value of <0.05 will be considered significant.

10.2 Secondary study parameter(s)

The correlation between FAPI PET/CT findings and lung function (DLCO and VC), 6-MWT, EQ5D and HRCT fibrosis findings will be assessed using Pearson's correlation coefficient or Spearman's rank-order correlation. Statistical significance between consecutive tests will be assessed using analysis of variance, paired t-test or Wilcoxon signed-rank test, as appropriate. A p-value of <0.05 will be considered significant.

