^{68}Ga -FAPI PET can therefore aid in the understanding of the pathophysiology of PASC with persistent pulmonary complaints. With ^{68}Ga -FAPI PET we aim to quantify the fibroblastic activity in relation to the percentage of interstitial lung abnormalities on high resolution computed tomography (HRCT), lung function testing including diffusing capacity of the lungs for carbon monoxide (DLCO) and vital capacity (VC), fibrotic and inflammatory blood markers, systemic and upper respiratory tract cellular phenotypes as determined by single cell RNA sequencing, 6-minute walking test (6-MWT) and self-reported daily impairments measured by EQ-5D questionnaire of patients with PASC at >3 months after hospital

discharge and, in case of persisting symptoms, at 8-10 months after ^{68}Ga -FAPI PET/CT scan.

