8.1.2 Secondary study endpoints

1. To relate the degree of Fibroblast Activation Protein expression at least 3 months after hospital discharge to DLCO and VC, ECM and inflammatory blood markers, systemic and upper respiratory tract cellular phenotypes, 6MWT and EQ-5D at the same time point.
2. To relate the degree of Fibroblast Activation Protein expression at least 3 months after hospital discharge to interstitial lung abnormalities on HRCT, 6MWT and EQ5D 8-10 months after timepoint T_0 in patients with persisting respiratory complaints.

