8.3.2 PET/CT imaging

To assess pulmonary fibrosis activity, we will perform ^{68}Ga -FAPI biodistribution studies in 20 post-COVID-19 patients using established protocols. After insertion of a peripheral intravenous catheter, each subject will undergo a PET and low dose CT (PET/CT) scan (Vision or QUADRA Biograph mCT, Siemens Medical Systems, Erlangen, Germany), from head to proximal lower limb 60 minutes following intravenous injection of 200 MBq ^{68}Ga -

FAPI. An HRCT scan will be performed immediately afterwards, on the same scanner. Total scanning time will be 15 minutes.

If HRCT, as ordered by attending pulmonologist as part of regular care, is repeated 11-13 months after hospital discharge for persisting pulmonary complaints, this data will be used for analysis.

PET analysis:

⁶⁸Ga-FAPI uptake as a measure of fibrosis activity in the lung will be evaluated by visual assessment of the active pulmonary ⁶⁸Ga-FAPI lesions. Increased ⁶⁸Ga-FAPI uptake will be compared with the muscle background uptake and defined as being positive when higher, and verified by follow-up with HRCT. For quantitative analysis, a specialized software platform from Hermes Hybrid 3D (Hermes Medical Solutions AB, Stockholm, Sweden) will be used. The mean and maximum standardized uptake value (SUV) and the metabolic active volume (MAV) normalized to body weight will be manually computed for the active pulmonary lesions and healthy tissues by drawing a 3-dimensional volume of interest. Multiplication of SUV_{mean} and MAV results in total lesion FAPI (TL-FAPI). Whole-lung FAPI-MAV (wIFAPI-MAV) can then be calculated by summation of MAV over all lung areas. Whole lung mean SUV (wSUV_{mean}) will be calculated as the mean of the SUV values of all five pulmonary lobes. These parameters will allow us to calculate whole lung TL-FAPI (wTL-FAPI) by multiplying wIFAPI-MAV with SUV_{mean}.

SUV_{max} ratio for the pulmonary hotspot will be defined as the quotient of the SUV_{max} of this lesion and the normal muscular tissue, and target-to-background ratio (TBR) for active pulmonary lesions will be calculated according to the formula: $TBR = tSUV_{max}/mSUV_{mean}$, where tSUV_{max} is the maximum SUV of lung lesion, and mSUV_{mean} is the mean SUV of muscle.

HRCT analysis:

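### Optional, low-cost addition to section 10.2: beside the raw correlation of T0 FAPI with follow-up HRCT and 6MWT, report one adjusted for the same measure at T0

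*Combined protocol and SAP*

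**What the plan says.** Section 8.1.2, endpoint 2, relates FAP expression at T0 "to interstitial lung abnormalities on HRCT, 6MWT and EQ5D 8-10 months after timepoint T_0", in patients whose respiratory complaints persist. Section 2 sets the matching objective.

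Section 10.2 names two kinds of analysis:

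- **Correlation.** "The correlation between FAPI PET/CT findings and lung function (DLCO and VC), 6-MWT, EQ5D and HRCT fibrosis findings will be assessed using" Pearson's or Spearman's coefficient. No covariate is mentioned.
- **Comparison over time.** "Statistical significance between consecutive tests will be assessed using analysis of variance, paired t-test or Wilcoxon signed-rank test, as appropriate". No FAPI term is named.

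Section 10.1 is also a two-variable correlation, and section 10.3 is marked not applicable. The introduction to section 10 sets the status of all of this: "Outcomes of primary and secondary study parameters will be exploratory outcomes". A p-value below 0.05 is nevertheless called significant in both 10.1 and 10.2.

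The T0 values exist. For HRCT, section 8.3.2 says: "An HRCT scan will be performed immediately afterwards, on the same scanner". Section 8.3.6 has every subject walk the 6MWT at the PET visit.

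Follow-up is conditional on persisting complaints and on a repeat HRCT ordered in regular care. Its timing is given in two ways. Section 8.3.2 uses an HRCT that "is repeated 11-13 months after hospital discharge for persisting pulmonary complaints, this data will be used for analysis", whereas sections 8.1.2, 8.3.3 and 8.3.6 count 8-10 months from T0.

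**The concern.** Endpoint 2 is the only part of the plan that links FAPI to later status. The rationale (section 1.1) is that CT does not reveal the pathogenesis and that FAPI imaging might, so a reader of the follow-up result will want to know whether FAPI says anything beyond the HRCT taken at the same visit. A raw correlation with the follow-up value cannot show that. It combines any relation between FAPI and later course with the T0 relation already tested in 10.1 and 10.2. The consecutive tests use the T0 values but, as written, do not bring in FAPI. No named analysis puts T0 FAPI, the T0 value and the follow-up value together.

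What is at stake is interpretation: a significant raw follow-up correlation could be read as prediction when it only restates the T0 finding.

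**Working it through.** **Plan's own figure.** There is none to reproduce. Section 4.4 sets 20 patients by convention, without a power analysis, and the documents give no correlations, reliability or follow-up n. All correlations below are assumptions; two-sided 0.05 is also assumed.

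**Model.** F = T0 FAPI, Y0 = the measure at T0, Y1 = the same measure at follow-up, all standard normal. Let a = corr(F, Y0) and b = corr(Y0, Y1), the stability. FAPI has no added value: F and Y1 are independent given Y0. There is no selection into follow-up.

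- Raw: corr(F, Y1) = a × b.
- Partial: [corr(F,Y1) − corr(F,Y0)·corr(Y0,Y1)] / √[(1 − a²)(1 − b²)] = (ab − ab)/… = 0.
- Critical |r| = t/√(t² + df), with df = n−2 (raw) or n−3 (partial). At n=10/15/20 this is 0.632/0.514/0.444 raw and 0.666/0.532/0.456 partial, so adjustment costs little here.

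**Percent significant, raw test** (simulation, 40,000 replicates per setting, n=10/15/20):

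| a / b | raw r = ab | Pearson | Spearman |
|---|---|---|---|
| 0.3 / 0.3 | 0.09 | 5.6/6.2/6.6 | 5.9/6.3/6.6 |
| 0.5 / 0.3 | 0.15 | 6.8/8.1/9.7 | 7.0/8.0/9.1 |
| 0.5 / 0.8 | 0.40 | 21.0/32.5/43.0 | 18.9/28.8/37.8 |
| 0.7 / 0.9 | 0.63 | 53.8/76.2/88.3 | 45.8/68.0/82.0 |

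The partial correlation rejects in 4.7-5.3% (Pearson) or 4.6-6.5% (Spearman). At n=6/8 the raw Pearson figures for the first three rows are 5.3/5.5, 5.7/6.4 and 12.0/16.3. At a=0 the figure is 5%.

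**Measurement error.** With reliability 0.7 in both measurements, at 0.6/0.9 and n=10/15/20, the partial test rejects in 7.9/10.4/12.9% (Pearson) or 8.9/11.4/13.7% (Spearman), against 26-54% for raw Pearson at n=10-20. Adjustment then removes most of the T0 relation, but not all.

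**Change score.** corr(F, Y1 − Y0) = (ab − a)/√[2(1 − b)] = −a·√[(1 − b)/2]. At 0.7/0.3 this is −0.7 × √0.35 = −0.41, significant in 22.4/34.9/46.2% with no added value, because Y0 enters with a negative sign.

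**Precision of the adjusted estimate.** The approximate 95% CI half-width around a partial Spearman of 0 is tanh(1.96·√[1.06/(n−4)]): 0.68/0.54/0.47 at n=10/15/20 and 0.89/0.77 at n=6/8. Power for a true partial correlation of 0.5 is 25/41/55% and 12/19% respectively.

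**Follow-up window.** Let T0 fall t months after discharge, t ≥ 3. One window is t+8 to t+10 months after discharge; the other is 11 to 13.

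- They are identical only if t + 8 = 11, that is t = 3.
- They overlap only if t + 8 ≤ 13, that is t ≤ 5. Later than that they are disjoint.

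**The case against.** The case against is strong on several counts.

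- **The planned test is valid.** The endpoint asks to relate FAPI to later measures, not to predict them or explain change, and all outcomes are exploratory. This stands. A reader might infer that the table shows an inflated false-positive rate. It does not: when a and b are non-zero, the raw correlation ab is real, so each rejection is correct for the planned quantity. The percentages are power for a true marginal correlation.
- **The inputs are assumed.** Section 1.3 allows match or mismatch between PET and HRCT, and section 1.1 calls the evolution of the abnormalities unknown, so the plan assumes neither a T0 correlation nor stability. At low stability the addition gains little. This stands.
- **Selection is ignored.** If the 10 of 20 patients with the highest follow-up value plus noise are kept (an assumed mechanism), raw rejection falls from 21% to 17% at 0.5/0.8 and from 54% to 41% at 0.7/0.9. If ordering the scan also depends on FAPI, it falls to 7% and 21%. The figures above may therefore overstate the effect, and adjustment does not cure selection.
- **The wording is open.** A reader might infer that 10.2 rules out any FAPI factor. It only names none; the factors of the analysis of variance are not stated.
- **The HRCT value at T0 is not one number.** The score in section 8.3.2 has several features, so one must be chosen.
- **The estimate will usually be inconclusive.** True, which is why it belongs beside the raw result with an interval.

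A reader might also infer that lung function is a follow-up measure, because section 1.1 lists "lung function testing including diffusing capacity of the lungs for carbon monoxide (DLCO) and vital capacity (VC") in a sentence that ends with assessment "in case of persisting symptoms, at 8-10 months after" the scan. That is one background sentence; the follow-up parts of sections 2 and 8.1.2 do not include lung function, so the point is not extended to it.

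**Conclusion.** This is an optional improvement, not the correction of a wrong analysis. The textual basis is firm: nothing in section 10 names an analysis that combines T0 FAPI, the T0 value and the follow-up value. The size is conditional. At n=10-20, with no added value of FAPI, the raw Pearson test would be significant in 6-10% at stability 0.3 and 21-43% at 0.5/0.8, against about 5% after adjustment. This assumes normal data, error-free T0 values and no selection. If FAPI is unrelated to the measure at T0, or the measure does not persist, there is little to gain. The plan cannot know this beforehand, which favours writing the addition down now.

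The conflict between the two follow-up windows is a separate matter, and real on the text alone. It bears on this analysis because it decides which HRCT counts as the follow-up value.

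**What to change.** In section 10.2:

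1. Keep the raw correlation.
2. Beside it, labelled exploratory and with a 95% CI, report the partial Spearman correlation of T0 FAPI (wTL-FAPI and wFAPI-MAV) with the follow-up value given the same measure at T0. Do this for 6MWT and for one HRCT measure fixed beforehand, for example overall extent of interstitial lung disease. Include EQ-5D only if a follow-up value is obtained; section 8.3.3 describes a repeat 6MWT but no repeat questionnaire.
3. Do not use follow-up minus T0 as a substitute.
4. State that the raw correlation alone does not show that FAPI predicts later disease, and that a null adjusted result does not show absence of added value.

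Separately, reconcile section 8.3.2 (11-13 months after discharge) with sections 8.1.2, 8.3.3 and 8.3.6 (8-10 months after T0).

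**Cost.** Wording only: T0 HRCT and 6MWT are already collected. The addition is 2 FAPI parameters × 2 measures = 4 estimates, or 6 with one EQ-5D score. Each costs one degree of freedom and has a wide interval, widest below n=10. Some residual confounding from error in the T0 value remains, and selection into follow-up is untouched.
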